Participants will be randomized to intervention or control groups using a minimization scheme which will adaptively weight probabilities of treatment assignment based on the distribution of age (≥ 40 vs. < 40), gender (male vs. female), and ethnicity (European/African/East Asian/South Asian/Latino/Other). This design has been adopted to minimize unintended covariate biases, which can plague smaller trials. Randomization will be implemented through a centralized database. The intervention will be delivered via automated e-mails, minimizing direct personal contact with the intervention group.

Controls

Upon completion of all three components of the baseline assessment, the control group will receive access to a GoodLife fitness centre of their choosing or if not specified, the location nearest to their home. For safety purposes, an orientation will be provided by GoodLife Fitness staff to all study participants. This will serve to demonstrate best practices within the gym, including how to

properly operate the fitness equipment, what the appropriate footwear and workout attire is, and general operating rules within the gym. To further ensure the safety of study participants when exercising, it will be emphasized that (1) exercises should be performed with some form of supervision when attempting a new exercise or heavy weight (e.g. a GoodLife Fitness staff member to spot), (2) to never perform types of exercises they may be uncomfortable with, and (3) to never attempt to exercise using an excessive amount of weight. Study participants may also consult GoodLife Fitness staff if they have questions about how to perform a specific exercise.

Intervention

In addition to a free gym membership for the duration of the trial (all participants, irrespective of randomization, will receive a free gym membership), the intervention group will receive (1) their genetic results, (2) personalized workout plan and (3) personalized meal plans, all of which will be delivered through a secure web portal accessible via smartphone or computer. See the “data privacy and security” section below for details regarding specific security measures for the web portal.

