All analyses conducted will follow the “Intention-to-treat” (ITT) principle to avoid biases due to differential adherence or loss-to-follow-up. In other words, no post-hoc exclusions will be made; study participants will be analyzed according to the group to which they were initially assigned even if they did not receive the intended treatment (e.g. due to injury during trial period impeding ability to exercise) or did not comply. Descriptive characteristics of each group will be summarized as the mean, standard deviation and 95% confidence-interval for continuous variables and using frequencies and percentages for categorical variables. Statistical tests will be two-sided, and between-group comparisons will be presented with 95% confidence intervals where possible. The statistical significance level set will vary depending on the number of statistical tests performed. Multiple hypotheses testing will be adjusted for within analyses of primary and secondary endpoints using a Bonferroni-corrected p-value threshold.

Baseline characteristics

Baseline characteristics will be compared using univariate regression to assess the balance of key risk factors between the intervention and control groups. Linear regression will be applied for continuous variables (age, blood pressure, waist-to-hip ratio, body fat percentage, total weekly

physical activity level, and dietary risk score) logistic regression for dichotomous variables (gender, smoking status, diabetes, dyslipidemia), and analysis of covariance (ANCOVA) will be applied for categorical variables exceeding two factor levels (ethnicity, hospital site). Intervention status will be the independent variable in the regression model. Differences in the mean or proportion of categories between groups will be considered statistically significant if the P-value is less than 0.05.

Primary Endpoints

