The primary endpoints are changes in physical activity levels as well as dietary risk score (DRS) from baseline to follow-up. Between-group differences in primary endpoints will be evaluated through linear regression. Weekly physical activity level will be represented as a continuous variable (frequency of strength training and aerobic exercise per week) for the primary analysis. Baseline characteristics found to be differentially distributed between intervention and control groups will be included as covariates in subsequent models. Between-group differences for changes in dietary risk score will be assessed through linear regression again adjusting for covariates. The significance threshold for physical activity levels and dietary health will be 0.025 given that two primary endpoints are tested.

Subgroup analysis will be conducted to explore whether changes in dietary health and physical activity levels differ based on key strata (age > 40 vs. age < 40, ethnicity, gender, baseline low/med/high physical activity levels and baseline dietary risk score tertiles). For example, it is conceivable that individuals who begin with the lowest activity levels and least healthy diets have the derive more benefit from personalized health recommendations, whereas others who already adhere to healthy lifestyle behaviours may have an attenuated response to our intervention.

Secondary Endpoints

Between-group differences in changes in levels of dyslipidemia (triglycerides), dysglycemia (fasting glucose), inflammation (C-reactive protein), blood pressure, measures of fitness (waist-to-hip ratio, circumference of thigh, calf, and bicep, body fat percentage) and overall cardio-metabolic risk as estimated by IHMRS will be analyzed using linear regression. Model covariates will include any baseline characteristics found to be differentially distributed between intervention and control groups. These analyses are considered exploratory and the significance threshold will thus be set at 0.05 for suggestive association and 0.005 (i.e. Bonferroni correction for 10 tests) for definitive association.

Technical Considerations

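### ANCOVA does not fit the baseline comparison of ethnicity and hospital site, yet its p-value decides whether they enter the primary and secondary models

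*Combined protocol and SAP*

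**What the plan says.** Under Data Analysis Plan, Baseline characteristics, the purpose and type of comparison are given as follows: "Baseline characteristics will be compared using univariate regression to assess the balance of key risk factors". Linear regression is assigned to continuous variables and logistic regression to dichotomous ones. For the rest, "analysis of covariance (ANCOVA) will be applied for categorical variables exceeding two factor levels (ethnicity, hospital site"). The direction is the same for every variable: "Intervention status will be the independent variable in the regression model". The criterion is "Differences in the mean or proportion of categories between groups will be considered statistically significant if the P-value is less than 0.05".

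Under Primary Endpoints the result is put to use: "Baseline characteristics found to be differentially distributed between intervention and control groups will be included as covariates in subsequent models". The second primary endpoint follows suit: "Between-group differences for changes in dietary risk score will be assessed through linear regression again adjusting for covariates". Secondary Endpoints repeats the rule: "Model covariates will include any baseline characteristics found to be differentially distributed between intervention and control groups".

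Under Randomization, ethnicity is a minimization factor with six levels: "ethnicity (European/African/East Asian/South Asian/Latino/Other"). Trial Population lists eight hospital sites; site is not a minimization factor.

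**The concern.** With arm as the predictor, ethnicity and site are the outcomes. ANCOVA models a continuous outcome, and a univariate comparison has no covariate to adjust for. The pairings of method and variable are sound for continuous and dichotomous variables and fail only for these two. No chi-square, Fisher or multinomial test is named anywhere in the plan.

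If the instruction is followed as written, the categories must be given numbers. They have no natural order, so the numbering is arbitrary and is not specified. The p-value then reflects the numbering as well as the data. This reaches beyond the baseline table because the same p-value decides whether ethnicity or site is adjusted for in the primary and secondary analyses.

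**Working it through.** **The plan's own figure.** Power Calculations gives 250 per arm, a difference of 0.32 SD, alpha 0.025 and 90% power; the Overview makes tests two-sided. The standardized difference is 0.32 / √(2/250) = 3.58. Subtracting the critical value 2.24 leaves 1.34, and Φ(1.34) ≈ 0.91. The stated 90% reproduces (90.9%), and this point does not affect it.

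**Dependence on coding.** The documents give no category counts, so this table is an assumption. Ethnicity, in the protocol's order:

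| Arm | Eur. | Afr. | E. Asian | S. Asian | Latino | Other | Total |
|---|---|---|---|---|---|---|---|
| A | 150 | 20 | 20 | 30 | 15 | 15 | 250 |
| B | 150 | 20 | 36 | 14 | 15 | 15 | 250 |

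- Pearson chi-square: only East Asian (expected 28 per arm) and South Asian (expected 22 per arm) contribute. 2 × 8²/28 + 2 × 8²/22 = 4.57 + 5.82 = 10.39 on 5 df, p = 0.065.
- Multinomial likelihood ratio: 10.59 on 5 df, p = 0.060.
- F test on numeric codes: the difference in mean code is 16 × (South Asian code − East Asian code) / 250 = 0.064 × (gap between the two codes). In the listed order the gap is 1, the SD of the codes is about 1.60 and the standard error is 1.60 × √(2/250) ≈ 0.143, so t ≈ 0.064/0.143 ≈ 0.45 and p = 0.66. With codes 1 and 6 for these two groups the gap is 5 and the difference is 0.32.
- Over all 720 numberings of these same data, p runs from 0.004 to 0.70, and 120 of the 720 (17%) fall below 0.05.

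**Error rate under the null.** 20,000 simulated trials, 250 per arm, simple randomization, one fixed coding. Assumed site shares: 5, 25, 20, 10, 20, 10, 4 and 6%. Assumed ethnicity shares: 70, 5, 7, 8, 4 and 6%.

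| Variable | Coded F test, P<0.05 | Chi-square, P<0.05 | Decisions differ |
|---|---|---|---|
| Site, 8 levels | 5.0% | 4.9% | 7.7% |
| Ethnicity, 6 levels | 5.0% | 4.8% | 7.3% |

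The coded test keeps its size but flags different data sets.

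**Missed imbalance.** One of eight sites holds 15% of one arm and 24% of the other, with 250 per arm and assumed sizes for the rest. Among trials that chi-square flags, the share missed by the coded test, as the imbalanced site moves through code positions 1 to 8, is 49, 71, 90, 91, 83, 62, 47 and 30%. The exact values shift with the assumed sizes; the range of roughly 30% to 90% is the usable result.

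**Effect on the primary test.** Simulation of the site gate, 4,000 trials per setting, with site assumed to explain 2% or 5% of outcome variance and alpha 0.025. Type I error was 2.3–2.6% with the coded gate and 2.3–2.5% with a chi-square gate. Power at 0.32 SD was 90.8–91.3% and 90.8–91.5%. The primary conclusion differed between the two gates in 0.1–0.4% of trials.

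**The case against.** The strongest reply is that this is a slip of wording. The plan never says that categories will be numbered, and its criterion speaks of proportions of categories, which suggests a chi-square-type comparison. If the model is turned round, with arm as outcome and ethnicity as factor, the F test on the table above gives p = 0.065, the same as chi-square to three decimals. That may well be what was meant. It does not settle the matter, because the stated direction rules it out and an analyst would have to depart from the text to reach it.

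Other parts of the reply stand. A reader might infer that the test is invalid in the sense of inflated error; it is not, since one fixed coding rejects in about 5% of null trials. A reader might also note that with 20 arbitrary codings at least one gives P<0.05 in about 38% of null trials. That describes a search over codings, which nothing in the plan proposes. Nor can it be said that site imbalance would usually be missed: a 91% miss rate is one end of the range, and the rate is below half in three of the eight positions. Any such imbalance arises by chance, because allocation is randomized.

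For ethnicity there is little to detect. In simulations of minimization on age, gender and ethnicity (assumed category mix, biased-coin probabilities 0.7, 0.8 and 0.9, 800 trials each), neither test flagged ethnicity in any trial.

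**Conclusion.** The point holds as a mismatch between method and variable with a minor consequence. The plan names a method that does not fit ethnicity or site, nothing elsewhere corrects it, and the p-value is the only stated gate for these two variables into the primary and secondary models. Only two of the 12 listed baseline variables (6 continuous, 4 dichotomous, 2 multi-category) are affected. Site is the more exposed, because it is not minimized.

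The sizes rest on assumed site and ethnicity distributions and on the literal reading that categories are coded numerically. A reader might infer that the primary result is in jeopardy. The documents do not support that: the simulated effect on the primary conclusion is well under 1% of trials, and the sample size and stated power are untouched.

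**What to change.** In Baseline characteristics, replace ANCOVA for ethnicity and hospital site with a chi-square or multinomial likelihood-ratio test, and state that it is for description only.

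In Primary Endpoints and Secondary Endpoints, remove the rule that baseline differences select covariates. Prespecify ethnicity, as a minimization factor, and site if wanted, as fixed categorical covariates. Changing the test alone would leave covariate choice to baseline p-values: with 12 independent tests at 0.05 the chance of at least one false flag is 1 − 0.95^12 ≈ 46%. That figure is illustrative, since the variables are correlated and minimization lowers it.

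The cost is SAP wording and (6 − 1) + (8 − 1) = 12 degrees of freedom at most, out of about 500. No change to the sample size is needed.

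### Choosing covariates by P<0.05 baseline tests usually leaves out the outcome's own baseline; fixing that term in advance would gain precision at no data cost

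*Combined protocol and SAP*

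**What the plan says.** All outcomes are changes from baseline to 3 months, analysed by linear regression. For the primary endpoints the Data Analysis Plan states: "Baseline characteristics found to be differentially distributed between intervention and control groups will be included as covariates in subsequent models". For the dietary score it adds: "Between-group differences for changes in dietary risk score will be assessed through linear regression again adjusting for covariates". The Secondary Endpoints section repeats the rule: "Model covariates will include any baseline characteristics found to be differentially distributed between intervention and control groups".

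The only criterion for a difference is in the Baseline characteristics section: "Differences in the mean or proportion of categories between groups will be considered statistically significant if the P-value is less than 0.05". The candidates are listed there too: "Linear regression will be applied for continuous variables (age, blood pressure, waist-to-hip ratio, body fat percentage, total weekly", continuing "physical activity level, and dietary risk score) logistic regression for dichotomous variables (gender, smoking status, diabetes, dyslipidemia", plus ethnicity and hospital site. That makes 12 variables.

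The secondary outcomes are given as "Between-group differences in changes in levels of dyslipidemia (triglycerides), dysglycemia (fasting glucose), inflammation (C-reactive protein), blood pressure, measures of fitness" and "waist-to-hip ratio, circumference of thigh, calf, and bicep, body fat percentage) and overall cardio-metabolic risk as estimated by IHMRS will be analyzed" by linear regression. The plan counts them as 10 tests.

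The Randomization section minimises on age (cut at 40), gender and ethnicity. No section fixes these factors, or the baseline value of the outcome, as covariates.

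**The concern.** In a randomised trial, baseline differences between arms are due to chance. A significance screen therefore admits a covariate because it happened to be imbalanced, however well or poorly it predicts the outcome. The strongest predictor of a 3-month value is usually the same measurement at baseline, and this rule seldom lets it in.

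At stake is the precision of both primary and all ten secondary comparisons. The covariate set also stays unknown until the baseline tests are run, and the plan does not say outright that the adjusted model is the one tested at 0.025.

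**Working it through.** **Inputs from the documents.** 250 per arm, two-sided alpha 0.025 per primary endpoint, difference 0.32 SD, stated power 90% (Power Calculations); baseline screen at P<0.05.

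**Inputs assumed.** The correlation rho between baseline and 3 months is not given; 0.3 to 0.9 is used. Unless stated otherwise: complete data, equal SDs at both visits, own baseline as the only candidate covariate.

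**1. The plan's own figure.** Noncentral t power with 250 per arm, d = 0.32 and alpha 0.025 is 90.8%. The stated 90% reproduces without adjustment if 0.32 is in SDs of change.

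**2. Counting the outcomes.** Own baseline is on the candidate list for five: activity, dietary risk score, blood pressure, waist-to-hip ratio and body fat. It is not listed for seven: triglycerides, fasting glucose, C-reactive protein, thigh, calf and bicep circumference, and IHMRS (diabetes and dyslipidemia appear only as yes/no variables). 5 + 7 = 12 = 2 primary + 10 secondary.

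**3. How often the term is omitted.** For a listed outcome, 1 - 0.05 = 95%. If the minimisation factors explain 5%, 10% or 20% of the baseline variance and are fully balanced, this rises to 95.6%, 96.1% or 97.2%.

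**4. Gain from always adjusting, 0.32 in SDs of change.** The variance ratio of adjusted to unadjusted change is (1 - rho^2)/[2(1 - rho)] = (1 + rho)/2. The adjusted effect size is 0.32/sqrt((1 + rho)/2), and the 95% CI narrows by 1 - sqrt((1 + rho)/2). The plan's rule was simulated with 4 million trials per scenario.

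| rho | variance ratio | plan's rule, power | always adjusted, power | gain (points) | CI narrower than unadjusted | rule's type I error |
|---|---|---|---|---|---|---|
| 0.3 | 0.65 | 92.0% | 98.6% | 6.5 | 19.4% | 0.019 |
| 0.5 | 0.75 | 91.7% | 97.0% | 5.3 | 13.4% | 0.021 |
| 0.7 | 0.85 | 91.3% | 94.8% | 3.5 | 7.8% | 0.022 |
| 0.8 | 0.90 | 91.1% | 93.6% | 2.4 | 5.1% | 0.023 |
| 0.9 | 0.95 | 91.0% | 92.2% | 1.2 | 2.5% | 0.024 |

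Gains are from unrounded values. The type I error is below 0.025 because the rule adjusts in just those trials where an unadjusted change test would reject too often under the null (15.0% of flagged trials at rho 0.3, 4.1% at rho 0.9).

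**5. Unequal SDs.** With k = follow-up SD / baseline SD, the variance ratio is (1 - rho^2)k^2/(k^2 + 1 - 2 rho k). The denominator minus the numerator is (1 - rho k)^2, so the ratio never exceeds 1, and it equals 1 when rho k = 1.
- rho 0.8, k 1.25: (0.36 x 1.5625)/(1.5625 + 1 - 2) = 0.5625/0.5625 = 1, no gain.
- rho 0.8, k 1.1: ratio 0.968, adjusted power 91.7%.
- rho 0.7, k 0.8: ratio 0.628, adjusted power 98.8%.

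**6. If 0.32 is in SDs of the level.** The effect size is 0.32/sqrt(2(1 - rho)) unadjusted and 0.32/sqrt(1 - rho^2) adjusted. Plan's rule against always adjusted: 79.7% and 93.3% at rho 0.3 (13.6 points), 91.7% and 97.0% at 0.5 (5.3), 99.2% and 99.7% at 0.7 (0.5), and about no difference above that.

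**7. Missing data.** Technical Considerations replaces missing continuous values by the mean over both arms. If 10% of follow-up values are imputed this way (an assumed rate), simulated power at rho 0.5 is about 85% under the plan's rule and 94.5% with own baseline always in the model.

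**The case against.** The strongest reply is that nothing fails. The rule is written in advance, its type I error is not inflated in the case simulated, and with complete data on the SD-of-change reading it meets the 90% target at every rho shown. Ten of the twelve outcomes are secondary, and the plan calls those analyses exploratory. All of this stands, and it makes the point one of efficiency.

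The size is also soft. Rho, equal SDs and the meaning of 0.32 are not settled by the documents: the cited SD is of weekly activity in MET-min, while the analysed endpoint is weekly exercise frequency. The simulated rule had one candidate, where the plan lists 12. The candidate list may not be exhaustive, since the Secondary Endpoints wording speaks of any baseline characteristics. Counting systolic and diastolic pressure separately makes the split 6 and 7. These limits affect the size. The direction holds: the large-sample variance ratio is never above 1.

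Three stronger readings are tempting but not supported:
- A reader might infer that baseline is ignored. It is not: every outcome is a change score, so only the covariate term is missing.
- A reader might infer data-dredging or inflated type I error. The selection uses baseline data under a fixed rule, and its error rate is 0.019 to 0.024 when own baseline is the only candidate.
- A reader might infer that this rule defeats the 90% power claim. With complete data, a shortfall appears only if 0.32 is in SDs of the level and rho is below about 0.47. With mean imputation power can fall below 90% on either reading, but the imputation causes that loss.

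**Conclusion.** The point holds as an improvement in precision that needs no new data, and it should be made. The P<0.05 rule captures almost none of the available gain: it lifts power from 90.8% to only 91.0-92.0% on the SD-of-change reading, where always adjusting gives 92.2% (rho 0.9) to 98.6% (rho 0.3) and a 95% CI 2.5% to 19% narrower than for unadjusted change. Those ranges rest on complete data and equal SDs and are not bounds: the gain is larger for k below 1 and vanishes at rho k = 1. On the SD-of-level reading it runs from 13.6 points at rho 0.3 to about zero above 0.7. That own baseline is never a candidate for the seven unlisted outcomes holds only if the list is exhaustive. Neither the validity of the tests nor the stated power is shown to be wrong.

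**What to change.** Replace the P<0.05 covariate rule, for primary and secondary endpoints, with one prespecified linear model: change on arm, baseline value of the same outcome, age group (40 and over against under 40), gender and ethnicity. Merge small ethnicity categories by a rule fixed before outcome data are seen. State that this is the model tested at 0.025 for both primary endpoints, and use the same form, each with its own baseline, for the 10 secondary endpoints. Label any unadjusted result as supportive. Keep the baseline comparison as description, with no role in choosing covariates.

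The cost is SAP wording. A change score already needs the baseline value, and the minimisation factors are recorded. The model has at most 8 extra terms (baseline 1, age group 1, gender 1, ethnicity 5). The lost degrees of freedom are negligible. Chance imbalance in the added terms inflates the variance by about 8/490 = 1.6%, where 490 = 500 - 2 - 8. That costs at most about 0.1 points of power at rho 0.3 and 0.4 at rho 0.9 if none of the terms is prognostic, and less under minimisation.

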All statistical analyses will be conducted in R version 3.4.0. Outlying values exceeding four standard deviations will be winsorized or removed if due to a data entry error. If a continuous variable is not normally distributed, then log transformation or quantile normalization will be applied. Missing values for continuous variables will be imputed based on the mean value across all samples with non-missing values including both intervention and control groups. For categorical variables, missing values will be imputed using the proportion of non-missing samples belonging to a given factor level to define the probability of assigning a study participant to that factor level.

Power Calculations

At a sample size of 500 participants (250 intervention and 250 control group), we estimate that we will have 90% power to detect a difference of 0.32 standard deviations between intervention

and control groups ($\alpha=0.025$). An alpha of 0.025 is used in lieu of the traditional value of 0.05 in order to account for multiple hypotheses testing of the two primary endpoints (physical activity and diet risk score). For physical activity, this is equivalent to a difference in ~ 50 MET-min/wk which translates to a difference of 12.5 minutes of moderate exercise or 6.75 minutes of vigorous exercise per week⁹. This power calculation is based on the work by Jurakic *et al.* (2009) who estimated average weekly physical activity levels in adult Croatians to be 3492 MET-min (SD=162.25) using the same validated questionnaire that will be used in the present trial¹². The translation of the dietary risk score is less straight-forward as the scoring system is comprised of disparate food habits that best predict acute myocardial infarction (e.g. salty meat vs. cooked vegetables). Granted, we will be well-powered to detect a 0.32 standard deviation in INTERHEART dietary risk score between intervention and control groups at $\alpha=0.025$.

Data Security & Privacy

Primary genetic data is defined as an individual's genotypic state generated directly from a laboratory instrument. Primary genetic data is highly sensitive personal information as it represents an individual's genetic code. Consequently, strict security measures will be employed to safeguard these data and mitigate the risk of confidentiality breach:

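### Replacing the fixed 0.025 threshold for the two primary endpoints with a Holm step-down would gain power within the same 5% family-wise limit; the present rule is valid, so this is an improvement and not a correction

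*Combined protocol and SAP*

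**What the plan says.** The Primary Endpoints section of the Data Analysis Plan names two endpoints ("The primary endpoints are changes in physical activity levels as well as dietary risk score (DRS) from baseline to follow-up") and gives both the same fixed level: "The significance threshold for physical activity levels and dietary health will be 0.025 given that two primary endpoints are tested". The Overview sets the general rule, "Multiple hypotheses testing will be adjusted for within analyses of primary and secondary endpoints using a Bonferroni-corrected p-value threshold", and also states "Statistical tests will be two-sided".

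Power Calculations follows the same rule. It says "An alpha of 0.025 is used in lieu of the traditional value of 0.05" because there are two primary endpoints, and that with 250 per arm "we will have 90% power to detect a difference of 0.32 standard deviations between intervention" and control groups.

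No section has a step-down, hierarchical or alpha-recycling rule. The plan gives no power for showing both effects and does not say whether the trial succeeds on one endpoint or needs both.

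**The concern.** Under single-step Bonferroni each endpoint faces 0.025 whatever the other shows. Suppose activity passes and diet comes in at p = 0.03. The plan must then call diet negative. Holm, with the same 5% family-wise ceiling, would call it positive. Once one endpoint has been correctly rejected, at most one true null is left, so 0.05 is enough for the remaining test. The fixed rule leaves that part of the error allowance unused.

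This matters because the plan gives each primary endpoint its own verdict and the primary objective covers both diet and exercise. A real effect in the second domain could go undeclared only because of the testing procedure chosen.

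**Working it through.** **Inputs from the documents.** 250 per arm, difference 0.32 SD, two-sided level 0.025, stated power 90% (Power Calculations; sidedness from the Overview). Two primary endpoints, taken as one p-value each, as the plan's own count implies.

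**Assumptions not in the documents.** Correlation between the two test statistics (range 0 to 0.8), complete data, and a true effect of 0.32 SD on both endpoints unless stated otherwise.

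**1. The plan's own figure.** The noncentrality is 0.32 × √(250/2) = 3.578. The two-sided critical values are 2.241 (level 0.025) and 1.960 (level 0.05).

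- Power at 0.025: Φ(3.578 − 2.241) = 0.909 (noncentral t, 498 df: 0.908).
- Power at 0.05: Φ(3.578 − 1.960) = 0.947 (noncentral t: 0.946).
- In reverse, for 90% power: n = 2 × (2.241 + 1.282)² / 0.32² = 242.4, so 243 per arm or 486 in all.

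The stated 90% with 500 participants is reproduced.

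**2. Power to show both, independent endpoints.**

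- Bonferroni: 0.9093² = 0.827.
- Holm needs the smaller p ≤ 0.025 and the larger p ≤ 0.05: 2 × 0.9093 × 0.9471 − 0.9093² = 1.722 − 0.827 = 0.896.

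**3. Power per endpoint under Holm, independent endpoints.** 0.9093 + (0.9471 − 0.9093) × 0.9093 = 0.944.

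**4. Over a range of correlations** (bivariate normal):

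| Correlation | Both, Bonferroni | Both, Holm | Gain (points) | Per endpoint, Bonferroni | Per endpoint, Holm |
|---|---|---|---|---|---|
| 0 | 82.7% | 89.6% | 6.9 | 90.9% | 94.4% |
| 0.3 | 83.7% | 90.0% | 6.3 | 90.9% | 94.1% |
| 0.5 | 84.7% | 90.4% | 5.7 | 90.9% | 93.8% |
| 0.8 | 86.9% | 91.5% | 4.6 | 90.9% | 93.2% |

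The chance of at least one significant endpoint is the same under both methods (99.2% at correlation 0, 95.0% at 0.8), because Holm's first step is the Bonferroni test.

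**5. Unequal effects.** Let one effect be 0.32 SD and the other 0.20 SD, independent. The smaller effect has noncentrality 0.20 × √125 = 2.236.

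- Bonferroni: Φ(2.236 − 2.241) = 0.498.
- Level 0.05: Φ(2.236 − 1.960) = 0.609.
- Holm: 0.498 + (0.609 − 0.498) × 0.909 = 0.599.

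Power for the smaller effect therefore rises from 50% to 60%.

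**6. Error rates** (simulation, 2 million draws per scenario).

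- Both nulls true: identical for the two methods, 4.95% at correlation 0 and 4.0% at 0.8.
- One null true, the other effect 0.32 SD: Bonferroni 2.5%; Holm 4.8% at correlation 0 and 4.1% at 0.8. By hand at correlation 0: 0.025 + 0.025 × 0.909 = 0.048.

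Holm stays at or below 5% in every scenario run, as its general proof requires.

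**7. Loss to follow-up.** The plan makes no allowance for it. Assuming 10% loss (225 per arm) with independent endpoints, power for both goes from 76.7% to 85.2%. At 20% loss (200 per arm) it goes from 69.1% to 79.3%. The levels fall, but the gain from Holm grows.

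**The case against.** The strongest reply is that nothing here is wrong. Fixed Bonferroni is valid, pre-specified and used consistently in the Overview, Primary Endpoints and Power Calculations, and the only power target the plan sets is met. All of that stands. It fixes the status of the point as an efficiency suggestion. It does not make the choice a matter of taste, because Holm never loses a rejection that Bonferroni would make.

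Second, the gain in power for both endpoints answers a goal that the plan does not state. If one significant endpoint is enough, Holm changes nothing. This also stands, so the headline size should not rest on the joint figure alone. The per-endpoint gain does not depend on how success is defined, since each endpoint is judged separately; at the design effect it is only 2 to 3 points.

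Third, a reader might infer that the change is wholly without cost or leaves every error rate as it was. It does not. The two procedures agree when both nulls are true, but differ when one effect is real and the other is null: the null endpoint's false-positive chance nearly doubles. The extra power comes from using error allowance that Bonferroni leaves idle.

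Fourth, a reader might extend the argument to the secondary endpoints, which carry a level of "0.005 (i.e. Bonferroni correction for 10 tests) for definitive association". The documents do not support making this part of the point. The plan calls those analyses exploratory and already grades them in two tiers, and no gain has been shown for them. The count of ten also depends on treating blood pressure as one test, although Table 2 lists systolic and diastolic.

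**Conclusion.** The point holds as a cheap improvement. For two primary endpoints, Holm has the same 5% upper limit on family-wise error as the planned rule, under any correlation, and is at least as powerful for each endpoint. With 250 per arm, complete data and 0.32 SD on both, the gain is about 2 to 3 points per endpoint and 4.6 to 6.9 points for showing both, over correlations from 0 to 0.8. It is about 10 points for a second effect of 0.20 SD (independent endpoints).

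The absolute levels are illustrative: the plan offers 0.32 SD as a detectable difference and not as an expected effect, and it gives neither a correlation nor a dropout rate. If power per endpoint were exactly 90%, the joint figures at correlation 0 would be 81.0% and 88.4%.

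A reader might conclude that the plan's multiplicity control is faulty, or that the trial falls short of its stated power. Neither follows: the 0.025 level is sound and the 90% is reproduced.

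**What to change.** Specify Holm before any unblinded results are seen; adopting it afterwards would not be credible.

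- **Primary Endpoints:** replace the fixed level with a rule such as: *The smaller of the two primary p-values is compared with 0.025; if it is met, the other is compared with 0.05 (Holm).*
- **Overview:** name the Holm procedure for the primary endpoints in place of the Bonferroni threshold. Otherwise the general rule there would contradict the amended section. The secondary-endpoint rule stays as it is.
- **Power Calculations:** keep the statement at 0.025, which becomes a lower bound on power per endpoint.

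The cost is two edited sentences, with no extra participants or data. The higher false-positive chance for a null second endpoint should be accepted knowingly. Simultaneous confidence intervals that match Holm are less simple than 97.5% Bonferroni intervals, but the Overview promises only ordinary 95% intervals, so no planned output is lost.
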